The exclusion criteria are: 1) pregnant or breastfeeding women; 2) abdominal pain lasting >96 hours before admission; 3) the possibility of poor oral intake for reasons other than AP; 4) Pancreatic neoplasm, endoscopic retrograde cholangiopancreatography or trauma etiology; 5) Chronic pancreatitis; 6) Randomization greater than 12 hours after admission.

Sample size

Given that historically the duration of hospitalization for mild AP at two hospitals is 7 days, a sample size of 120 patients (60 in each group) will be necessary to be recruited using a 10% drop-out rate, 80% power and 95% significance level to detect a two-day difference in total length of hospital stay between the study groups.

Randomisation

In each centre participants will be divided into two groups receiving one of the two study treatments. The allocation of participants to the different groups will be carried out based of predefined randomization lists created separately for each recruiting centre. The randomization lists will be prepared with a block size of 2 and with an allocation ratio of 1:1.

Duration

The planned starting date of the study is June 1st, 2017 and the planned finishing date of the study is December 31st, 2018.

Intervention

Based on the currently available guidelines, oral refeeding can be started early for patients with mild and moderate AP. Additionally, with an LFSD appeared safe and provided more calories. Therefore, both groups can be regarded as being treated within accepted practice recommendations. In this study, EORF with LFSD will be the intervention. Patients will be randomized to group A or PADI diet (EORF with LFSD) or fasting group.

Groups

In group A (PADI), the oral refeeding will be started after admission. Patients will receive a low fat solid diet with more and less 1500 calories, 35 g fat day.

In group B (fasting), the oral diet will be reintroduced in a traditional stepwise manner until the symptoms, signs, inflammatory parameters of AP have resolved.

General patient management

General treatment intimated by the IAP / APA guideline will be used.

All patients will receive adequate intravenous fluid resuscitation based on their individual hemodynamic parameters and fluid balanced. The patients will be monitored daily for gastrointestinal symptoms, abdominal pain, total intake/output, nutritional parameters, and laboratory findings.

Endpoints

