The primary endpoint is length of hospitalization. Several secondary endpoints such as pain, the duration of fasting, tolerance to food, relapse rate, degree of transitional abdominal distension and/or abdominal pain and/or vomits after the first ingestion of oral food, multiorgan failure, pancreatic infection, hyperglycemia, nutritional parameters, mortality and quality of life will be determined to elucidate more detailed differences between the groups. The feasibility, safety and quality checks required for high quality evidence will be adhered.

Monitored parameters during hospitalisation

There will be a large variety of parameters monitored during the study: medical history, physical examination, laboratory test, diagnostic imaging, therapy, complications, interventions. The data collection will be done in the form A. This form will contain parameters collected on admission, parameters every day during hospital admission and contain parameters 1 month after hospital discharge.

Data management and statistical analyses

The investigator will ensure that the data in the form A are accurate, complete and legible. Detailed data flow will be described in a Data Management Plan. Data from completed form A will be validated under direction of the Data Manager according to a Data Cleaning

Plan. Any missing, or inconsistent recordings in the form A will be referred back to the investigator of each centre. The Data manager is a biostatistician.

Study populations

Three analysis populations will be defined:

Safety Analysis Set (SAS): all patients enrolled in the study.

Per Protocol Set (PPS): all enrolled patients who finished the study conforming to the requirements of the study protocol.

Intention to Treat (ITT): all randomized participants who start on a treatment, excluding consent withdrawals.

Withdrawal of a subject from Per Protocol Set

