Any participants / investigators and Data manager can submit recommendations for dropouts from the PPS group with reasons given to the coordinator. The coordinator will discuss all the recommendations all the information and, if the alteration in the protocol would be expected to have any bearing on the interventions and outcomes of the study, the patient will not be included in the final pre-protocol analysis. Automatic dropout from per-protocol group shall be ordered if: 1) any of the exclusion criteria are diagnosed during the course of AP; 2) parameters for answering the primary endpoints are missed; or 3) serious medical reasons nor related to pancreatitis occur.

Applied software

Statistical analysis will be performed using SPSS 21 statistical packages. Pages Mac will be used for reporting.

Statistical methods

Baseline patient and disease characteristics will be analyzed using descriptive analysis. Demographic and baseline characteristics will be summarized for the overall study population. Continuous variables will be described by mean, median, SD and ranges and categorical variables will be described by absolute and relative frequencies. A graphical presentation of efficacy variables will be prepared. Descriptive statistics for both the primary and secondary parameters will be analyzed similarly. Mean changes (with 95% CI) from baseline to end-of-study visit will be presented. Chi-square test will be applied to compare proportions between the different groups. Survivals will be investigated using the Kaplan-Meier analysis method, while subgroup comparisons will be performed using the Chi-square or Fisher's exact test, as appropriate. For safety data, descriptive statistics and individual listing of adverse events will also be presented.

Centres

The trial will start in six centres:

1. Consorci Sanitari del Garraf - Hospital Residencia San Camil
2. Hospital Universitari Joan XXIII de Tarragona
3. Hospital Clinic de Barcelona

In all centre the coordinator will make an audit of the centre and will report to Data Manager.

Publication policy

Centres providing more than 20 patients can provide one authors to the authorship list. Every additional 20 patients will give the opportunity to nominate an additional author.

Feasibility and safety

The diet is a general protocol for the treatment of AP.

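### Removal from the per-protocol set rests partly on open nominations and an undefined test, with no deviation list, deadline or masking, so the per-protocol comparison of length of stay is exposed to selective removal

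*Combined protocol and SAP*

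**What the plan says.** The section 'Withdrawal of a subject from Per Protocol Set' gives two ways out of the PPS.

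- **Discretionary route.** Nomination: "Any participants / investigators and Data manager can submit recommendations for dropouts from the PPS group with reasons given to the coordinator". Review: "The coordinator will discuss all the recommendations all the information". Test: "if the alteration in the protocol would be expected to have any bearing on the interventions and outcomes of the study". Consequence: "the patient will not be included in the final pre-protocol analysis" (read here as per-protocol).
- **Automatic route.** There are three rules, beginning "Automatic dropout from per-protocol group shall be ordered if: 1) any of the exclusion criteria are diagnosed during the course of AP". The other two cover missing data for the primary endpoint and serious medical reasons unrelated to pancreatitis.

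Other sections that bear on this:

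- Intervention: "Patients will be randomized to group A or PADI diet (EORF with LFSD) or fasting group". No blinding of any person is described anywhere.
- Endpoints: "The primary endpoint is length of hospitalization".
- Centres: "In all centre the coordinator will make an audit of the centre and will report to Data Manager".
- Study populations (under Data management and statistical analyses) defines a Safety set, a PPS and an ITT set. Neither that section nor Statistical methods says which set carries the primary comparison.

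**The concern.** A per-protocol exclusion is safe when it is settled by rules fixed in advance and applied to everyone. The discretionary route lacks those protections. It names no deviations that qualify, so the test can cover almost any departure. It depends on someone choosing to nominate, so two patients with the same deviation can be treated differently. It has no cut-off before discharge or database lock, and no masking of arm or stay is described.

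Direction matters as well. A group A patient who does not tolerate the diet may both depart from it and stay longer, and would readily meet the test. Removing such patients would favour the trial's main hypothesis of a shorter stay without anyone acting in bad faith. The documents do not show that this would happen, but nothing in the procedure prevents it.

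At stake is the PPS comparison of length of stay. Because no primary set is named, that comparison cannot be set aside as merely supportive.

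**Working it through.** **1. What each step of the route controls**

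| Step | What the plan provides | What is absent |
|---|---|---|
| Who nominates | Three named groups, with reasons | A duty to screen every patient in both arms |
| Who reviews | The coordinator | Masking to arm or stay; a statement of who takes the final decision |
| Criterion | Expected bearing on interventions and outcomes | A list of deviations |
| Timing | Nothing | A cut-off before outcomes are known |
| Role of the PPS | One of three sets | A statement of which set is primary |

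Solid diet and fasting are visible to patient and staff. Length of stay is fixed and known at discharge. Nomination and review can therefore take place with both known.

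**2. An SD for the illustration**

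The Sample size section gives a 7-day historical stay, a two-day difference, 80% power, a level read as two-sided alpha 0.05, 10% drop-out and 60 per group. It gives no SD, so 120 cannot be reproduced from the stated inputs alone. Solving for the SD that fits:

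- n per arm = 2 × (1.96 + 0.84)² × SD² / 2².
- With SD = 3.7, n rounds up to 54, and 54 / 0.90 = 60 per arm, 120 in total.
- The implied SD is about 3.71 days (4.18 if the test were one-sided).

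I use SD 3.7 as an assumption.

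**3. Worst-case removal**

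Both arms have mean 7 days, SD 3.7 and 60 patients, with no true difference. The k longest stays are removed from one arm only and a two-sided t-test is applied, with 20,000 simulated trials per case.

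| Removed from one arm | Shift, normal | Type I error | Shift, lognormal | Type I error |
|---|---|---|---|---|
| 0 | 0.00 | 4.9% | 0.00 | 5.0% |
| 3 of 60 | −0.38 days | 9.7% | −0.53 days | 14.5% |
| 6 of 60 | −0.71 days | 20.4% | −0.88 days | 31.3% |

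As fractions of the two-day target: 0.38/2 = 19%, 0.53/2 = 26%, 0.71/2 = 36% and 0.88/2 = 44%.

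The shift equals k × (mean stay of those removed − 7) / (60 − k). Working back, the three patients removed average about 7 + 0.383 × 57/3 = 14.3 days (normal) or 7 + 0.528 × 57/3 = 17.0 days (lognormal). The six average about 7 + 0.710 × 54/6 = 13.4 or 7 + 0.877 × 54/6 = 14.9 days.

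**4. Range over the unknown SD**

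In the normal case the shift is proportional to SD.

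- SD 3.0: 0.383 × 3.0/3.7 = 0.31 days for three removals; 0.710 × 3.0/3.7 = 0.58 days for six.
- SD 5.0: 0.383 × 5.0/3.7 = 0.52 days for three; 0.710 × 5.0/3.7 = 0.96 days for six.

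The normal model allows some negative stays, so it serves only as a reference. The documents give no distribution for length of stay.

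**The case against.** The strongest reply is that the route is narrower than it may look and touches only one of three sets. Much of that is right.

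- **Nominators.** They are three named groups who must give reasons. This stands, but a reason can be written after the stay is known.
- **Who decides, and blind to what.** A reader might infer that a single unblinded coordinator takes the decision. The text says the coordinator discusses the recommendations and then turns to the passive voice. It does not state the coordinator's blinding status. Visible diets, centre audits and the absence of any masking make the inference reasonable, but it remains an inference.
- **What the test asks.** A reader might infer that patients are to be removed because of their own stay. The criterion concerns the expected effect of the deviation on the study's interventions and outcomes. It does not direct anyone to the patient's result.
- **Scope.** The route leaves the ITT and Safety sets untouched. With ITT as primary this would affect a sensitivity analysis only. The plan does not say that ITT is primary.
- **Size.** Larger shifts can be had by choosing the stays removed. Three 21-day stays give (420 − 63)/57 = 6.26, a shift of 0.74 days; six 14-day stays give (420 − 84)/54 = 6.22, a shift of 0.78 days. The documents supply no such stays, and for three removals 0.74 exceeds the 0.38 to 0.53 obtained at SD 3.7. Six is 10% of one arm, but the drop-out allowance in the sample size is not a forecast of PPS removals. The 7-day figure is for mild disease, while moderate cases are also enrolled.

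The missing list, deadline, masking and common screening all remain.

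**Conclusion.** The concern holds for the PPS. The discretionary route, as written, permits removal after arm and length of stay are known, under a test with no defined content. The result is a PPS comparison that can be biased, not one that must be. A reader might go further and conclude that the trial's result is untrustworthy, or that following the procedure necessarily corrupts the PPS. The documents support neither conclusion.

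The size is about 0.4 to 0.5 days for three removals and 0.7 to 0.9 days for six. This rests on an assumed SD of 3.7 days, no true difference, and the longest stays all removed from one arm. It marks what the rule leaves possible and does not predict what would occur. How much it matters depends on a choice the plan does not make, namely which analysis set is primary. The change should be made, as it costs little.

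**What to change.** 1. Replace the nomination route and its open-ended test with a closed list of objective major deviations. Define the list separately for each arm, because a diet deviation in one arm may be adherence in the other. Write it before enrolment, or at least before any outcome by arm is seen.
2. Apply the list systematically to every randomised patient from form A, using only the adherence and eligibility fields needed. Withhold length of stay as far as practicable. Omitting the discharge date alone is not enough, because form A has entries for each hospital day and their number reveals the stay.
3. Freeze the PPS list before length of stay is summarised by arm.
4. Report removals by arm, with reasons and length of stay.
5. Name the ITT set as primary and the PPS as a sensitivity analysis.

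The cost is protocol wording plus a structured review of form A for all patients. There are two downsides. An unforeseen deviation that is not on the list stays in the PPS. Full masking to arm is not possible for diet deviations, so the protection comes mainly from the fixed list, its application to everyone and the freeze.

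### No planned analysis of length of stay uses centre or admission data, and no baseline table by arm is specified, so precision already available to the trial is left unused

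*Combined protocol and SAP*

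**What the plan says.** The Endpoints section is clear about the target: "The primary endpoint is length of hospitalization".

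On baseline data, the Statistical methods section has two sentences: "Baseline patient and disease characteristics will be analyzed using descriptive analysis", followed by "Demographic and baseline characteristics will be summarized for the overall study population". Neither mentions a display by arm, and no other section supplies one.

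The comparative methods named in the same section carry no covariate: "Chi-square test will be applied to compare proportions between the different groups", and "Survivals will be investigated using the Kaplan-Meier analysis method, while subgroup comparisons will be performed using the Chi-square or Fisher's exact test, as appropriate". Length of stay is to be described, but no test or model is named for it. Baseline values appear in one other place: "Mean changes (with 95% CI) from baseline to end-of-study visit will be presented". That cannot reach the primary endpoint, because length of stay has no baseline value.

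Two other sections bear on this. Under Randomisation, each centre has its own list, and "The randomization lists will be prepared with a block size of 2 and with an allocation ratio of 1:1". Under Monitored parameters during hospitalisation, the plan says of form A: "This form will contain parameters collected on admission", along with daily and one-month data.

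**The concern.** Centre is built into the allocation and admission data are collected, yet neither is used in comparing length of stay. This has two consequences.

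First, separate lists with small blocks keep the arms nearly equal in number within each centre. Differences between centres in typical stay therefore largely cancel out of the treatment difference. An unadjusted standard error still counts them as noise. It is then too large, the confidence interval too wide and the test conservative.

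Second, admission variables that predict stay could reduce the residual variance. The trial mixes mild and moderate disease and does not stratify on severity, so some of the variation in stay may be predictable at admission.

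The missing by-arm table is a smaller matter of reporting. Without it a reader cannot see who was enrolled in each arm. That is worth seeing in a trial of feeding against fasting, with blocks of 2 and no described masking or concealment.

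**Working it through.** **Inputs from the protocol (Sample size).** Total 120, or 60 per arm; 10% drop-out; 80% power; a two-day difference; a significance level written as 95%, read here as two-sided 0.05. The standard deviation (SD) is not given.

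**Assumed.** R², the share of within-arm variance in stay explained by centre and admission covariates. The documents give no value, so a range of 5% to 30% is shown.

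**Step 1: the plan's own figure.** Without an SD, 120 cannot be reproduced directly, so the SD is back-solved. Evaluable per arm: 60 × 0.9 = 54. Then

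SD = 2 / [(1.960 + 0.842) × √(2/54)] = 2 / (2.802 × 0.1925) ≈ 3.71 days.

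As a check, SD 3.7 needs 54 per arm, and 54/0.9 = 60 per arm, which is 120 in total. A one-sided reading would imply 4.18 days.

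**Step 2: adjustment.** Residual SD = 3.71 × √(1 − R²). Power = Φ(2 / [residual SD × √(2/54)] − 1.960). The 95% half-width is 1.96 × residual SD × √(2/54). The last column is the recruited total that would give 80% power.

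| R² (assumed) | Residual SD | Power | Half-width (days) | Total for 80% |
|---|---|---|---|---|
| 0 | 3.71 | 80.0% | 1.40 | 120 |
| 0.05 | 3.62 | 82.0% | 1.36 | 116 |
| 0.10 | 3.52 | 84.0% | 1.33 | 110 |
| 0.20 | 3.32 | 87.9% | 1.25 | 98 |
| 0.30 | 3.10 | 91.8% | 1.17 | 86 |

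These are normal approximations. A t-based check agrees to within one percentage point. Centre itself uses 2 or 5 degrees of freedom (the Centres section announces six centres and lists three), out of 108 − 2 = 106.

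**Step 3: what ignoring centre does.** Suppose centre alone explains R² and is balanced by the lists. The unadjusted standard error is then too large by the factor 1/√(1 − R²): 1.03 at 5% and 1.20 at 30%. The actual two-sided type I error is 2 × [1 − Φ(1.960/√(1 − R²))], and power is Φ(0.842/√(1 − R²)).

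| R² from centre (assumed) | Actual type I error | Power, unadjusted | Power, adjusted |
|---|---|---|---|
| 0.05 | 0.044 | 80.6% | 82.0% |
| 0.10 | 0.039 | 81.3% | 84.0% |
| 0.20 | 0.028 | 82.7% | 87.9% |
| 0.30 | 0.019 | 84.3% | 91.8% |

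So the gain from 80% in step 2 applies in full to variance explained by admission covariates that are not stratified. For variance explained by centre the starting point is slightly higher and the gain smaller, but the error rate is also wrong, on the conservative side.

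**Step 4: how far the SD matters.** Because the SD was solved to give 80%, the power figures in step 2 depend only on R². If the true SD were 3.0, 4.0 or 5.0 days, unadjusted power with 54 per arm would be 93%, 74% or 55%, and the gain would start from there.

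**The case against.** **The baseline sentence may simply name the population described.** It does not say that arms will be pooled or not shown. The same section says that endpoint statistics will be handled similarly, and the endpoints plainly are to be compared between groups. This stands. A reader might infer that the plan forbids a by-arm table; the text supports only that none is specified.

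**Chance imbalance is not bias.** This also stands. The type I error and confidence interval of a randomised comparison already allow for it. A reader might infer that an unseen imbalance in severity would invalidate the result; it would not. Sizing the harm through a strong prognostic factor is also delicate. A factor adding 5 days and present in 15% to 30% of patients would by itself explain 25 × p(1 − p)/3.71² = 23% to 38% of the variance, so it cannot be combined with an R² of 10% or 20%. No such effect is in the documents.

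**Blocks of 2 are a randomisation matter.** Correct. A baseline table neither prevents nor corrects selective enrolment, and adjustment deals only with recorded factors. A reader might infer that every second allocation was foreseeable. That requires recruiters to know the block size and the preceding allocation; the documents do not say who holds the lists. Nor would an imbalance prove selection: at 60 per arm, a given continuous covariate differs by more than 0.2 SD by chance about 27% of the time.

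**No primary test is named, so nothing has been left out of it.** The absence of a primary analysis is indeed the larger gap. But whoever fills it must decide on centre and covariates, and should do so before seeing data.

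**The covariates may not exist at randomisation.** This limits the remedy. Form A's fields are not listed, and the severity classification is named without a time point. The per-protocol rules foresee exclusion criteria, some of them aetiologies, coming to light during the illness.

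**Conclusion.** The point holds as a loss of precision and a reporting gap, not as bias. The plan specifies no by-arm baseline display, and no analysis of length of stay uses centre or admission data. An unadjusted comparison would be valid but, where stay differs between centres, conservative: a nominal 0.05 becomes 0.044 to 0.019 if centre explains 5% to 30% of the variance. Adjustment would move power from 80% to between about 82% and 92% over the same range of total R². At the low end the gain is only about two points.

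The direction follows from the design whenever centre or the chosen covariates predict stay. The size rests on an SD back-solved from the sample size and on assumed values of R²; neither is in the documents. The adjustment carries most of the value, and the table adds transparency.

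**What to change.** In Statistical methods, when the primary analysis of length of stay is written:

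- Pre-specify that the comparison is adjusted for centre and for a short, fixed list of variables recorded before randomisation. Age is an example. Include severity class and aetiology only if form A records them before allocation; values settled later in the admission could be affected by the assigned diet.
- Report the unadjusted comparison as supportive.
- Tabulate baseline characteristics by arm and overall, without significance tests.

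This is a free improvement: a few sentences and one regression model, with no extra patients or visits, provided that the list keeps to items already recorded before randomisation. Any concern about predictable allocation has to be dealt with in the randomisation itself.

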Since no unknown drugs/therapy are used in the study, no adverse or serious adverse events are expected that would be attributable to the intervention during the trial.

Discussion

We report a prospective, randomized, controlled trial to study the effects of EORF with LFSD in AP. The current studies and meta-analysis suggest that EORF should be beneficial but we don't know the optimal timing and starting criteria. Our main hypothesis is that EORF with LFSD is well tolerated and leads to a shorter total length of hospitalization. The aim of the study will be evaluated the efficacy and feasibility of immediate oral feeding as compared to traditional fasting in patients with mild and moderate pancreatitis.

Ethics

The study has been approved by the relevant organization: Comitè Ètic d'investigació d'la Fundació Union Catalana d'Hospitals. Codi CEIC 17/05.

Dissemination

This study will provide strong evidence as to whether EOR with LFSD is beneficial in the clinical management of mild and moderate AP. The results of this trial will be published in an open access way and disseminates among medical societies.

Conclusion

This study provides the stronger evidence concerning the optimal timing and starting criteria for EORF with LFSD.

References

3. Working Group IAP/APA Acute Pancreatitis Guidelines. IAP/APA evidence-based guidelines for the management of acute pancreatitis. *Pancreatol*. 2013;13(4 Suppl 2):e1-15. doi: 10.1016/j.pan.2013.07.063.

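### The plan prespecifies no between-arm test, effect estimate, confidence interval or primary analysis set for length of hospitalization, the endpoint that sizes the trial

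*Combined protocol and SAP*

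**What the plan says.** The Endpoints section is clear: "The primary endpoint is length of hospitalization". The Sample size section plans 120 patients (60 per group) with 80% power and 10% drop-out "to detect a two-day difference in total length of hospital stay between the study groups", from a historical stay of 7 days. The Discussion adds: "Our main hypothesis is that EORF with LFSD is well tolerated and leads to a shorter total length of hospitalization".

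The Statistical methods section says of the primary endpoint only "Descriptive statistics for both the primary and secondary parameters will be analyzed similarly". The other methods it names are:

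- an interval estimate, for change over time within patients: "Mean changes (with 95% CI) from baseline to end-of-study visit will be presented"
- a between-group test, for categorical outcomes: "Chi-square test will be applied to compare proportions between the different groups"
- a time-to-event method, with no test attached: "Survivals will be investigated using the Kaplan-Meier analysis method"
- chi-square or Fisher's exact test for subgroup comparisons.

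Under Study populations the plan states "Three analysis populations will be defined" (safety, per protocol and ITT) and does not say which one carries the primary analysis. The ITT set leaves out randomised patients who do not start treatment and those who withdraw consent. The Randomisation section uses a separate list for each centre, and centre appears in no analysis.

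**The concern.** A trial sized on a difference in days should say in advance how that difference will be estimated and tested, and in whom. Here the reader has to guess. A t-test, a rank test, a test on log days and a time-to-discharge analysis are all defensible for hospital stay. They can give different answers on the same data, and choosing among them afterwards raises the false-positive rate.

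The analysis set is equally open. Under the section on withdrawal from the per-protocol set, the coordinator decides some exclusions case by case, and the text does not say that this is done blind to arm or outcome.

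Two smaller matters belong to the same paragraph of the plan. No rule says how an in-hospital death counts in a length of stay, although mortality is a secondary endpoint. And the factor used to organise the randomisation lists is absent from the analysis.

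**Working it through.** **1. Can any named method supply the comparison?**

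| Method in the plan | Attached to | Compares stay between arms? |
|---|---|---|
| Mean, median, SD, range | Continuous variables | No, description only |
| 95% CI | Change from baseline | No, stay has no baseline value |
| Chi-square | Proportions | No, stay is in days |
| Chi-square or Fisher | Subgroups | No |
| Kaplan-Meier | Survival | No, discharge is not mentioned and no test is attached |

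The documents refer to a Data Management Plan and a Data Cleaning Plan, but to no further analysis plan that might hold the missing text.

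**2. What the stated sample size implies.** No SD is given, so 120 cannot be reproduced from the plan's own inputs. It can be inverted. Take two-sided alpha 0.05 (sidedness is not stated), 80% power and 60 × 0.9 = 54 evaluable per arm:

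SD = 2 / [(1.960 + 0.842) × √(2/54)] = 2 / (2.802 × 0.1925) = 3.71 days.

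With the exact t-test the value is 3.68. Check: n = 2 × 2.802² × 3.7² / 2² = 53.7, so 54 per arm; 54/0.9 = 60, total 120. The figure fits a comparison of two means at an unstated SD near 3.7. The simulations below assume 3.67.

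**3. Does the choice of test matter?** Inputs: 54 per arm, means 7 and 5 days, 10,000 simulated trials per row. The shapes are assumed. In the equal-CV rows, 3.67 is the control SD and group A has 3.67 × 5/7 = 2.62.

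| Shape of stays | t-test power | Rank test power | Tests disagree |
|---|---|---|---|
| Gamma, equal SD | 80.6% | 90.8% | 11.0% |
| Gamma, equal CV | 90.4% | 86.9% | 5.5% |
| Lognormal, equal SD | 80.2% | 96.2% | 16.2% |
| Lognormal, equal CV | 91.2% | 93.2% | 4.9% |

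Disagreement over the same shapes is 1-7% at an assumed SD of 3 and 11-27% at 4.5. Neither test is better throughout.

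**4. Cost of choosing afterwards.** With both arms at mean 7 and SD 3.67 (20,000 replicates), taking the smaller of the two p-values gives type I error of 6.4% (gamma) and 6.6% (lognormal); repeat runs lay between 6.0% and 6.8%. Adding a t-test on log days gives about 7%.

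**5. Centre.** Inputs: 108 patients, three or six equal centres, 1:1 within centre, total SD held at 3.67. The between-centre SD is assumed. Pairs are for three/six centres.

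| Centre SD | Power without centre | Power with centre | Type I error without centre |
|---|---|---|---|
| 0.5 day | 81.0% / 80.2% | 81.3% / 80.6% | not run |
| 1 day | 81.3% / 80.7% | 82.6% / 82.4% | 4.6% / 4.1% |
| 2 days | 85.7% / 85.2% | 90.6% / 91.4% | 3.2% / 2.6% |

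At 2 days the CI is 2.64 / 2.72 days wide without centre and 2.34 with it. A centre SD of 2 days means that centre explains 2²/3.67² = 4/13.5, about 30%, of the variance.

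**6. In-hospital deaths.** One death in an arm of 54, counted as an assumed 3 days to death, moves the arm mean by (3 − 7)/54 = −0.07 or (3 − 5)/54 = −0.04 day, in favour of that arm. Counted as an assumed 30-day longest stay, it moves the mean by (30 − 7)/54 = 0.43 or (30 − 5)/54 = 0.46 day against the arm.

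**The case against.** The best defence is that the Sample size section already fixes the contrast: a two-day difference between groups, with a stated power and significance level. Statistical methods also promises means and SDs. If these are given by arm, anyone can compute a mean difference and its CI. This stands as far as it goes. A reader might infer that the plan makes the primary comparison impossible, or that no test is intended. The documents do not support that, since a power calculation presupposes a test. What is missing is prespecification: no test, sidedness, SD or estimator is named, and the text does not say that stay will be summarised by arm.

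A second defence reads Kaplan-Meier as time to discharge. The wording concerns survival, mortality is listed as a separate endpoint, and no comparison is attached.

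Third, the demonstrated harm is modest. Type I error reaches 6-7% only if someone reports the most favourable p-value, and the disagreement rates rest on an assumed SD and assumed shapes. That also stands. The freedom to choose the analysis set may matter more, but it was not quantified.

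Two further readings go too far. One is that omitting centre biases the result: it does not. It makes the test conservative, and visibly so only at a centre SD near 2 days, for which the documents give no support. The other is that naming the ITT set would settle the population: as defined, that set is not all randomised patients.

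**Conclusion.** The gap is real and should be closed before any outcome data are seen. It follows from the text alone: the primary endpoint is assigned descriptive statistics and nothing else, and no analysis set is chosen for it. The severity rests on that, because the comparison the trial is powered for is not prespecified.

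The numerical consequences are moderate and conditional. At an assumed SD near 3.7 days with skewed stays, two reasonable tests disagree in about 5-16% of trials, and picking the smaller p-value gives 6-7% type I error instead of 5%. Centre is a secondary matter, worth 0-2 points of power at a centre SD of 0.5-1 day. Only near 2 days is it material: about 85% versus 91% power, with unadjusted type I error about 3%. None of this shows that the sample size is wrong or that anyone intends a selective analysis.

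**What to change.** Add to Statistical methods:

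> Primary analysis: difference in mean hospital days (group A minus group B) with 95% CI, from a linear model with arm and randomising centre, two-sided alpha 0.05. Population: all randomised patients with a recorded length of stay who have not withdrawn consent to use of their data, analysed as randomised whether or not they started the assigned treatment. The per-protocol analysis is supportive. Sensitivity analysis: rank test stratified by centre, with in-hospital deaths given the worst rank. In-hospital deaths are reported by arm. If any occur, the mean difference is shown with deaths counted as days to death and again with deaths set to the longest observed stay.

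Deaths are shown both ways because days to death alone lets an early death favour its arm. The mean difference comes first because the trial is sized in days.

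The cost is one paragraph and slightly more analysis work, with no new data and no change in sample size. The centre term uses 2 degrees of freedom with three centres or 5 with six. The drawback is power: for skewed stays with equal SDs the mean comparison has about 80%, against 91-96% for the rank test. A rank test fixed in advance as primary would also close the gap, but it would not give a difference in mean days. The population still leaves out patients with no recorded stay, so their number should be reported by arm.

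As a side note, the Centres section announces six centres and lists three. The two should be reconciled so that the centre term is defined.
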